8.2. Statistical Analyses

The efficacy endpoints will be analyzed according to the cohorts specified in [Section 2](#).

8.2.1. Analysis of Efficacy Endpoints

The duration of cytogenetic, hematologic, and molecular response analyses are based on the full analysis set for the subset of B1871006 patients who respond for the respective endpoint. The K-M method, as described in [Section 8.1](#), will be used provided most responding patients transferred to B1871040 remain on treatment until progression or loss of response. The percentage of MR⁴, MMR, MCyR, CCyR, and PCyR and CHR and major hematologic response (MHR)/OHR (advanced patients only) for the respective endpoint, along with confirmed losses and censored patients still on-treatment will be summarized.

The time to transformation analysis is based on the full analysis set for the B1871006 patients. Cumulative incidence of transformation adjusting for the competing risk of treatment discontinuation due to any reason without transformation, as described in [Section 8.1](#), will be used. The percentage of transformation without treatment discontinuation and the percentage of treatment discontinuation due to any reason without transformation will be summarized. The specific disease stage transformation (accelerated or blast phases) will also be listed.

The PFS analysis is based on the full analysis set for the B1871006 patients. The K-M method, with or without unsatisfactory response as assessed by the investigator as an event and cumulative incidence of on-treatment progression or death adjusting for the competing risk of treatment discontinuation due to any reason without the event, as described in [Section 8.1](#), will be used. For K-M, the percentage of on-treatment death or progression, with or without unsatisfactory response as an event, will be summarized. For cumulative incidence, the percentage of on-treatment death or progression without treatment discontinuation and the percentage of treatment discontinuation due to any reason without on-treatment progression and death will be summarized.

The OS analysis is based on the full analysis set for all patients. The K-M method, as described in [Section 8.1](#), will be used. The number of deaths and causes of death will be summarized. Time on study from date of randomization for B1871008 patients and date of first dose for B1871006 patients to date of last contact, and reasons for discontinuing participation will also be summarized.

The percentage of patients with emergent mutations will be summarized.

Missing values and incomplete data will be handled as described in [Section 7](#) of this analysis plan.

Listings for all efficacy data will also be provided.

No COVID-19 related efficacy analyses will be performed as efficacy is only summarized for data up through 10 years after start of the parent study and all patients enrolled in B1871040 except one reached 10 years of follow-up prior to the March 11, 2020 COVID-19 anchor date and all China patients reached 10 years of follow-up prior to their January 9, 2020 anchor date. A summary of missing molecular and cytogenetic data before and after the anchor dates will be summarized for patients enrolled in B1871040.

A listing of COVID-19 related study discontinuations will be provided.

8.2.2. Analysis of Safety Endpoints

The safety analysis set will be used for all safety analyses unless specifically stated otherwise. The safety endpoints will be analyzed according to the cohorts specified in [Section 2](#) and also analyzed as a pooled set of all treated patients from B1871006 and B1871008.

8.2.2.1. Baseline Characteristics

Demographic, medical history, and other baseline characteristics will not be summarized for B1871040 as this information resides solely in the parent study databases. This summary information will be taken directly from the B1871006 and B1871008 clinical study reports.

8.2.2.2. Treatment and Compliance

Descriptive statistics for continuous exposure variables treatment duration and cumulative received dose, and received dose over time (% receiving 600, 500, 400, 300, 200, or 0 mg at specific time points) will be calculated.

The number and percentage of patients with at least one dose reduction due to AE, dose delay due to AE, and escalation to 600 mg will be summarized. The number and percentage of patients who experienced more than 1 event will also be summarized.

The number and percentage for reasons for treatment discontinuation will be summarized and listed. A listing of COVID-19 related treatment discontinuations will be provided.

8.2.2.3. Laboratory Evaluations, Vital Signs, and Cardiac Evaluations

The incidence of clinical laboratory, QTcF/QTcB, and LVEF abnormalities by maximum toxicity categorized by NCI CTC V3.0 grade will be presented at baseline, during the treatment period, and post treatment period.

Laboratory values that are outside the normal range also be flagged in the data listings. Any out-of-range values that are identified as being clinically significant will be presented in a data listing. PCIs for ECG, LVEF, vital signs and body weight will also be flagged in listings.

A summary of missing safety data before and after the anchor dates will be summarized for patients enrolled in B1871040.

8.2.2.4. Laboratory Evaluations of Special Interest

The number and percentage of maximum on-treatment grade 0 through 4 for ALT, AST, platelets, neutrophils, and hemoglobin will be summarized. Descriptive statistics for time to first event, duration of any grade event, and cumulative duration of grade 3/4 events will be calculated for each of these parameters.

8.2.2.5. Non-study Medications

A listing of non-study medications data will be reported.

8.2.2.6. Death

The number of deaths within 30 days of last dose and cause of these deaths will be summarized.

8.2.2.7. Adverse Events

The number and percentage of AEs listed below will be summarized overall and by MedDRA body system and PT. Sorting will be done alphabetically by body system and then by decreasing frequency of PT.

- TEAEs;
- AEs leading to treatment discontinuations;
- TEAEs leading to dose reductions;
- TEAEs leading to dose delays;
- TEAEs by maximum toxicity grade (grades 1 to 5);
- TEAEs of higher toxicity grades (grades 3 or 4);
- TEAEs related to test article;
- Serious adverse events (SAEs);

- COVID-19 related TEAEs.

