Compared with imatinib, bosutinib was associated with higher incidences of Grade 3-4 gastrointestinal toxicities, including diarrhea (12% vs. 1%), vomiting (3% vs. 0%) and abdominal pain (1% vs. <1%), although these adverse events were usually transient and manageable. Notably, diarrhea occurred mostly in the first 1-2 months of therapy and improved or subsided spontaneously over time. The rates of Grade 3-4 non-hematologic toxicities were $\leq 1\%$ in both arms of the study. Grade 3-4 elevations of alanine aminotransferase (23% vs. 4%), aspartate aminotransferase (12% vs. 4%) or lipase (11% vs. 6%) were more frequent among patients treated with bosutinib compared to imatinib. Of those patients experiencing Grade 3-4 elevations in transaminase levels in the bosutinib arm of this study, 91% were rechallenged. Of these patients, 80% did not experience subsequent elevations in transaminase levels that merited treatment discontinuation. Overall, 14% of patients were discontinued from bosutinib treatment due to unacceptable transaminase elevations. Grade 3-4 neutropenia, thrombocytopenia and anemia in the bosutinib and imatinib arms were 10% vs. 24%, 14% vs. 15% and 8% vs. 8%, respectively, indicating that bosutinib is at least as safe as imatinib regarding hematologic toxicity.

Ph+ Leukemia

Pooled safety data are reflected below (with a cutoff date of 15 November 2010). A total of 870 Ph+ leukemia patients across multiple, global Pfizer-sponsored clinical trials received at least 1 dose of single-agent bosutinib. These patients were either newly diagnosed Ph+ chronic phase CML, or were patients with resistant or intolerant Ph+ chronic, accelerated, or blast phase CML or Ph+ acute lymphoblastic leukemia (ALL). Of these patients, 248 are from the Phase 3 study in previously untreated CML patients, 570 and 52 are from two Phase 1/2 studies in previously treated Ph+ leukemias. The median duration of therapy was 16.6 months (range: 0.03 to 30.4 months) in the Phase 3 study, 11 months (range: 0.03 to 55.1 months), and 5.5 months (range: 0.3 to 30.4 months), in the Phase 1/2 studies respectively.

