9.7. Safety Analysis

Treatment-emergent AE (defined as any event increasing in severity from parent study baseline, or any new event starting during bosutinib therapy or within 30 days of the last bosutinib dose) incidence rates will be described both with and without regard to causality. The frequency of occurrence of overall toxicity, categorized by toxicity grades, will be described. Listings of laboratory test results collected at baseline and during the study will be generated and descriptive statistics summarizing changes in laboratory tests over time will be presented.

The incidence of diarrhea from the 2 parent studies and the incidence of diarrhea from extension study will be tabulated in order to compare the clinical and commercial formulations of bosutinib.

The pharmacokinetic analysis (collected for all patients except those from sites in China) will compare the C_{trough} of bosutinib in this study to C_{trough} of previous studies.

All patients dosed in the parent Studies B1871006 and B1871008 will be included in the safety analyses. Data from the two parent studies will be combined with the data from this study for the analysis of safety.

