6.2. Safety Endpoints

Treatment-emergent adverse events (TEAE) were defined as any event increasing in severity from baseline or any new event starting during bosutinib therapy or within 30 days of the last dose of study drug.

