8.2.2.8. Adverse Events of Special Interest

The number and percentage of maximum treatment-emergent CTCAE grade events and successful rechallenge for ALT, AST, thrombocytopenia (including MedDRA PT Platelet Count Decreased), neutropenia (including PT Neutrophil Count Decreased), anemia (including PT Hemoglobin Decreased), diarrhea, nausea, and vomiting will be summarized. Descriptive statistics for time to first event, duration of any grade event, and cumulative duration of grade 3/4 events will be calculated for each of these parameters.

The number and percentage of maximum treatment-emergent CTCAE grade events over time for diarrhea will be summarized. Only patients receiving treatment within a given time period will be included in the denominator for this time period. The incidence relative to the first dose of both the parent studies and the first dose of B1871040 will be calculated separately. Furthermore, the incidence relative to the last dose of bosutinib from the parent studies will also be calculated in order to see the percentage of patients experiencing diarrhea during the last 6 months prior to enrolling in B1871040. Time to first event in B1871040, defined as any new event in B1871040 or any increase in severity for ongoing events from B1871006 or B1871008, and duration of B1871040 events will also be summarized.

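### General adverse events are tabulated only as crude percentages over very unequal time on bosutinib, so the figures can be confounded by exposure and cannot show how risk changes over time

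*SAP*

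**What the plan says.** SAP 8.2.2.7 covers TEAEs, SAEs, grade 3/4 events, related events and events leading to dose changes or discontinuation. For all of them the measure is the same: "The number and percentage of AEs listed below will be summarized overall and by MedDRA body system and PT". SAP 8.2.2 presents safety by cohort and "also analyzed as a pooled set of all treated patients from B1871006 and B1871008".

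The TEAE definition in SAP 6.2 includes "any new event starting during bosutinib therapy or within 30 days of the last dose of study drug", so the risk window is each patient's own time on drug plus 30 days. Protocol 1.2.2 gives exposure at a November 2010 cutoff: "The median duration of therapy was 16.6 months" in the Phase 3 study and 11 months in B1871006, with a minimum of 0.03 months in both. Under SAP 2.1 patients stay in the study until the last one reaches 10 years from first dose, so those dosed earlier can pass 10 years. SAP 8.2.1 limits efficacy summaries to 10 years; no such limit is stated for safety.

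Some time-related summaries do exist. SAP 6.2.7 and 8.2.2.8 add time to first event, event duration and total time at grade 3/4 for adverse events of special interest, and SAP 6.2.3 and 8.2.2.4 do the same for five laboratory parameters. For diarrhea alone, SAP 8.2.2.8 specifies a table over time in which "Only patients receiving treatment within a given time period will be included in the denominator for this time period". SAP 8.2.2.2 summarises treatment duration and cumulative dose separately from the adverse events.

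**The concern.** The study has no primary endpoint. The first endpoint in Protocol 2.2 is long-term safety, expressly including how often adverse events occur and when. Protocol 9.7 says that TEAE "incidence rates will be described both with and without regard to causality", but the SAP turns these into percentages of patients treated. Neither document gives adverse events a person-time denominator, and SAP 8.1.4 names Kaplan-Meier and competing-risk methods only for efficacy endpoints.

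A percentage accumulated over a window that varies so widely mixes how often an event occurs with how long patients were watched. The cohorts range from first-line chronic phase to blast phase, will be read side by side, and are also merged into one pooled column. If exposure differs between them, a cohort difference may come from time on drug, or a real difference may be hidden by it. Within a cohort, one cumulative figure cannot separate a risk confined to the first year from one that continues into year 8.

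**Working it through.** **1. The plan's own measure.** The crude percentages in Protocol 1.2.2 reproduce as patients with an event divided by patients treated. Pooled: 248 + 570 + 52 = 870 and 848/870 = 97.5%, as stated. B1871006: 454/570 = 79.6% (stated 80%) and 117/570 = 20.5% (stated 21%).

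**2. Spread of exposure.** The minimum is 0.03 months × 30.4 = 0.9 day. Ten years is 3,652.5 days, so the ratio is 3,652.5 / 0.912, about 4,000. Exposure above 10 years is inferred from the closing rule; no observed maximum is given.

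**3. Steady events.** The documents give no hazard, so a range is assumed. With constant hazard r per patient-year and the same exposure of t years for everyone, crude % = 1 − exp(−r·t).

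| Assumed rate per 100 patient-years | 11 months | 16.6 months | 10 years |
|---|---|---|---|
| 2 | 1.8% | 2.7% | 18.1% |
| 5 | 4.5% | 6.7% | 39.3% |
| 10 | 8.8% | 12.9% | 63.2% |

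The underlying rate is identical within each row.

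If exposure instead varies exponentially with mean m years, crude % = r / (r + 1/m). At 5 per 100 patient-years this is 0.05/2.05 = 2.4% for a mean of 0.5 years and 0.05/0.25 = 20.0% for a mean of 5 years. The exposure-adjusted rate is 5.0 per 100 patient-years in both.

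**4. Early events.** Suppose all risk falls in the first 2 months and 80% have the event by then. The monthly hazard is −ln(0.2)/2 = 0.805. The crude percentage is 55.3% at 1 month, and 80.0% at 2 months, 11 months and 10 years alike. Protocol 1.2.2 places most diarrhea in the first 1 to 2 months, so later exposure hardly changes its percentage.

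**5. Does exposure explain the reported study differences?** Scale the B1871006 percentages (grade 3 or higher, treatment-related) from 11 to 16.6 months by 1 − (1 − p)^(16.6/11) and compare them with the B1871008 bosutinib arm (grade 3-4).

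| Event | B1871006 | Scaled | B1871008 reported |
|---|---|---|---|
| Thrombocytopenia | 20.5% | 29.3% | 14% |
| Neutropenia | 10.2% | 15.0% | 10% |
| Diarrhea | 7.7% | 11.4% | 12% |
| ALT increased | 6.3% | 9.4% | 23% |

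Exposure could account for the diarrhea difference, but not for the other three. For thrombocytopenia the shorter-exposed study has the higher percentage. Its crude ratio is 20.5/14 = 1.5. The implied constant rates are −ln(1 − 0.205)/(11/12) = 0.25 and −ln(1 − 0.14)/(16.6/12) = 0.11 per year, a ratio of about 2.3. Crude figures can thus understate a difference as well as create one.

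This is a direction check only. The exposure medians and the event percentages come from different cutoffs, and relatedness is not stated for B1871008.

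**6. Do the existing time summaries fill the gap?** Time to first event is to be described with ordinary descriptive statistics and no stated censoring method. Read that way it covers only patients who had the event, and it depends on length of follow-up itself. Cardiac, vascular and renal toxicity are listed in SAP 6.2.7 but are missing from the eight events named in SAP 8.2.2.8. Only diarrhea has a denominator that changes with time on treatment.

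**The case against.** The strongest reply is that the study is descriptive. SAP 4.1 and 4.2 plan no hypotheses or decision rules, and SAP 6.2.6 drops the tiered adverse event approach because there is no comparator. Safety is shown by cohort, so only the pooled column mixes blast-phase with chronic-phase exposure, and treatment duration is reported for anyone who wants to read it beside the percentages. Much of this stands. It limits the harm, but a reader still cannot recover a rate or a time pattern from a crude percentage and a separate summary of duration.

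Three stronger readings are tempting, and the documents do not support them:

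- A reader might infer that all adverse event reporting is crude. It is not: events of special interest have time-to-first-event and duration summaries, and diarrhea has a by-period table.
- A reader might infer that cohort differences mainly reflect time on drug. No exposure by cohort is given, cohorts also differ in disease phase and line of therapy, diarrhea is mostly early, and thrombocytopenia runs the other way.
- A reader might infer that the longest-surviving cohorts will look most toxic. The same thrombocytopenia figures (21% at a median of 11 months, 14% at 16.6 months) count against that as a general statement.

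It is also fair to say that the illustrative hazards are not from the documents, and that the two documented medians alone give a modest contrast, such as 8.8% against 12.9%.

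**Conclusion.** The point holds for the general adverse event tables. They are crude percentages over very unequal windows, so for steadily accruing events they can be confounded by exposure and cannot describe risk over time. That cardiac, vascular and renal events accrue in this way is a possibility; the documents do not establish it.

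Under a constant hazard and equal exposure, the same rate can appear roughly 7 to 10 times larger at 10 years than at 11 months (63.2/8.8 = 7.2; 18.1/1.8 = 10.1). For front-loaded events the effect is close to nil. The actual size in this study cannot be computed, because neither document gives patient-years by cohort.

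This is a cheap improvement that would let the study report what its first endpoint asks for. It does not invalidate the planned tables.

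**What to change.** - **SAP 8.2.2.8:** extend the diarrhea by-period table, with its on-treatment denominator, to every adverse event of special interest in SAP 6.2.7, by year and by cohort. This includes cardiac, vascular and renal toxicity, whose definitions the SAP already promises before database lock.
- **SAP 8.2.2.7 and 8.2.2.8:** beside the crude percentages, add first events per 100 patient-years at risk, by cohort and pooled. Define time at risk to match the TEAE window, from first dose to the first event or to 30 days after last dose, whichever is earlier.

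The cost is extra tables. Event dates and treatment duration are already collected, so no new data are needed. Exposure-adjusted rates assume a constant hazard and dilute front-loaded toxicity in long-treated patients, so for such events they must be read with the by-year table. The by-year table has its own limit, which a footnote should state: later denominators contain only patients who remained on bosutinib.

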8.2.2.8. Adverse Events of Special Interest

The number and percentage of maximum treatment-emergent CTCAE grade events and successful rechallenge for ALT, AST, thrombocytopenia (including MedDRA PT Platelet Count Decreased), neutropenia (including PT Neutrophil Count Decreased), anemia (including PT Hemoglobin Decreased), diarrhea, nausea, and vomiting will be summarized. Descriptive statistics for time to first event, duration of any grade event, and cumulative duration of grade 3/4 events will be calculated for each of these parameters.

The number and percentage of maximum treatment-emergent CTCAE grade events over time for diarrhea will be summarized. Only patients receiving treatment within a given time period will be included in the denominator for this time period. The incidence relative to the first dose of both the parent studies and the first dose of B1871040 will be calculated separately. Furthermore, the incidence relative to the last dose of bosutinib from the parent studies will also be calculated in order to see the percentage of patients experiencing diarrhea during the last 6 months prior to enrolling in B1871040. Time to first event in B1871040, defined as any new event in B1871040 or any increase in severity for ongoing events from B1871006 or B1871008, and duration of B1871040 events will also be summarized.

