- k. Diarrhea information will be recorded by the patient in the patient diarrhea card provided at the baseline visit. Completed cards will be collected after the first 3 months of treatment in this extension protocol.
- l. Follow-up will be conducted every 3 months from last dose of bosutinib. Long-term follow-up information will be collected via visit or telephone contact until the last patient reaches 10 years 524 weeks of follow-up, with one month of treatment=28 days for study purposes) from first dose of bosutinib (including the time on parent study). Serious adverse events occurring to a patient after the active reporting period has ended should be reported to the Sponsor if the investigator becomes aware of them; at a minimum, all serious events that the investigator believes have at least a reasonable possibility of being related to study drug are to be reported to the Sponsor.
- m. Pharmacokinetic Data: One pre-dose PK sample per patient (except those at Chinese sites) will be drawn, to be collected at first possible occasion after at least 2 weeks of uninterrupted dosing at steady state dose level.
- n. Contraceptive Check: patients of child-bearing potential will be required to verbally affirm the use of 2 highly effective methods of contraception until at least 28 days after the last dose of bosutinib. This conversation will be documented in the patient's source document.
- o. Dispensing or prescribing of bosutinib at least every 6 months, or more frequently as indicated.
- p. Data collection of either cytogenetic or residual molecular response testing. (Molecular response monitoring using reverse transcriptase polymerase chain reaction (RT-PCR) measurement of BCR-ABL fusion transcript levels in on peripheral blood may be performed in lieu of monitoring via cytogenetics, once molecular response is achieved, and according to standard of care and current treatment guidelines at investigative site).

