7.2.2. Special Recording of Diarrhea Events

EMA has required that ad hoc analyses are conducted in order to evaluate the incidence of diarrhea after study patient's transition to the bosutinib commercial formulation. To satisfy this request, a diarrhea card will be provided to the patients to collect the details of diarrhea events during the first three months on study treatment (see [Appendix 2](#)).

Diarrhea cards will be provided to all patients at the baseline visit. The cards will be collected at the Month 3 study visit; data reported by the patient will be reviewed by the investigator and recorded in the eCRF.

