8.1.2. Eliciting Adverse Event Information

The investigator is to record on the CRF all directly observed AEs and all AEs spontaneously reported by the study subject/[parent(s)/legal guardian/legally acceptable representative]. In addition, each study subject/[parent(s)/legal guardian/legally acceptable representative] will be questioned about the occurrence of AEs in a non-leading manner.

8.1.3. Withdrawal From the Study Due to Adverse Events (see also the [Subject Withdrawal](#) section)

Withdrawal due to AEs should be distinguished from withdrawal due to other causes, according to the definition of AE noted below, and recorded on the CRF.

When a subject withdraws from the study because of an SAE, the SAE must be recorded on the CRF and reported, as appropriate, on the CT SAE Report Form, in accordance with the Requirements section above.

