Appendix 2. Patient Diarrhea Card

Guidelines for the Management of Diarrhea for Participants in the bosutinib Extension Study

**Please be sure you understand these instructions BEFORE you leave the office
and discuss with your study doctor if you need to obtain
antidiarrheal medication before you go home.**

Data obtained thus far from patients receiving bosutinib including your own experience from your participation in study B1871006 or B1871008 show that diarrhea is the most common side effect you may have while receiving bosutinib. It has also been showed that diarrhea events, although frequent, are mainly low grade in severity, don't last long, occur predominantly in the first month of bosutinib treatment, and managed by appropriate concomitant medications given for short duration.

We do not anticipate any specific change in gastrointestinal disorders including diarrhea, however we are interested in additional characterization of diarrhea after extended treatment and helping to ensure appropriate management of any new episode of diarrhea.

Treating diarrhea as soon as it starts may prevent it from getting worse. Your study doctor may tell you to take antidiarrheal medication(s) with the first loose stool or diarrhea. Please contact your study doctor as soon as possible if you have an episode of diarrhea. If you are dizzy or weak because of diarrhea, come to the office or go to the hospital immediately.

Information to provide

When calling the study doctor to report an event of diarrhea you should provide as much of the information below as possible, in order to help your study doctor to assess your diarrhea and decide on the best treatment:

- Number of stools per day as compared to your normal bowel habits;
- Presence of diarrhea during the night;
- Presence of fever, dizziness, abdominal pain/cramping or weakness;
- What the stool looks like, that is, watery, bloody or mucousy;
- When you took your last dose of study drug;
- Any other information that could explain your diarrhea (change in diet/food, recent travel, contact with other people experiencing vomiting and/or diarrhea).

We will also provide you with a specific card which will help you to capture any relevant information occurring at the time of a diarrhea event.

Recommendations

1. Changes to your diet

If you have diarrhea:

- Stop all lactose-containing products (milk, yogurt, cheese...);
- Drink 8 to 10 large glasses of clear liquids per day;
- Eat frequent small meals;

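### The diarrhea card covers only the first 3 months after the formulation switch, and the SAP comparison does not separate or account for that period

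*SAP*

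**What the plan says.** **Purpose.** Protocol 9.7 sets up the comparison of the clinical and commercial formulations: "The incidence of diarrhea from the 2 parent studies and the incidence of diarrhea from extension study will be tabulated in order to compare" them. SAP 6.2.7 summarizes diarrhea characteristics separately for the parent studies and for B1871040, to the same end. Protocol 7.2.2 ties the exercise to an EMA request.

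**Analysis.** SAP 8.2.2.8 plans diarrhea by maximum grade over time: "The incidence relative to the first dose of both the parent studies and the first dose of B1871040 will be calculated separately". It adds a look-back from the last parent-study dose, "in order to see the percentage of patients experiencing diarrhea during the last 6 months prior to enrolling in B1871040". No post-switch periods are fixed.

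**Collection around the switch.** Under Protocol 7.2.2, "a diarrhea card will be provided to the patients to collect the details of diarrhea events during the first three months on study treatment". The footnotes to the Schedule of Activities say: "Completed cards will be collected after the first 3 months of treatment in this extension protocol". An extra Month 3 visit is arranged for this (Protocol 6.2). Of the card contents, 7.2.2 says: "data reported by the patient will be reviewed by the investigator and recorded in the eCRF". The leaflet in Appendix 2 adds: "Please contact your study doctor as soon as possible if you have an episode of diarrhea".

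**Collection otherwise.** Protocol 8.1.2 requires that observed and spontaneously reported events go on the CRF and that each patient "will be questioned about the occurrence of AEs in a non-leading manner". No other elicitation method is described.

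**Not said.** The SAP does not mention the card, give a rule for card-sourced events, or note any change in collection. Neither document says how diarrhea was elicited in B1871006 or B1871008.

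**The concern.** The card, the leaflet and the Month 3 visit all start on the day the patient changes to the commercial tablet. A before/after comparison at that date therefore changes two things at once: the formulation and, apparently, how hard the study looks for diarrhea. Matching the windows on length and time on drug does not remove the second change.

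The outcome is plausibly sensitive to solicitation. Protocol 1.2.2 reports treatment-related diarrhea in 454 patients in B1871006, with Grade 3 or higher in 44. So (454 - 44)/454 = 90% had nothing worse than Grade 2, and mild episodes are the ones most easily missed by general questioning.

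At stake is the reading of a regulatory commitment. An excess in the first months could be taken for a transient effect of the commercial tablet when it reflects the card. Pooled over a longer post-switch period, the same excess would be diluted and harder to recognize.

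**Working it through.** The documents state no expected diarrhea rate, sample size or power for this comparison, so there is no planned figure to reproduce. The check has two parts.

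**1. What the text establishes**

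- The card covers the first 3 months of the extension only: stated.
- Later extension months rely on routine questioning: this is the only other method described. The leaflet's request to contact the doctor has no stated 3-month limit, so some prompting may continue.
- The parent studies had no card: implied, because the card is introduced to answer the EMA request after the switch, but not stated.
- Card entries become adverse event records: likely, since they go through the investigator to the eCRF and Protocol 8.1 and 8.1.2 require all non-serious and spontaneously reported events on the CRF. The receiving form is not named.

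**2. Possible size, by assumption**

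Let T be the true 6-month incidence, the same before and after the switch, with constant hazard, and h = -ln(1 - T). Let s be capture with the card and c capture by routine questioning, taken first as equal before the switch and after Month 3.

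- Pre-switch 6 months: 1 - exp(-h c)
- Post-switch 6 months: 1 - exp(-h (s + c)/2)
- Months 0-3: 1 - exp(-h s/2)
- Months 3-6: 1 - exp(-h c/2)

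With T = 25%, h = 0.2877. For s = 95% and c = 60%: pre = 1 - exp(-0.1726) = 15.9%; post = 1 - exp(-0.2877 × 0.775) = 20.0%; ratio 1.26.

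| c (T = 25%, s = 95%) | Pre, 6 mo | Post, 6 mo | Ratio | Months 0-3 | Months 3-6 |
|---|---|---|---|---|---|
| 40% | 10.9% | 17.6% | 1.62 | 12.8% | 5.6% |
| 60% | 15.9% | 20.0% | 1.26 | 12.8% | 8.3% |
| 80% | 20.6% | 22.3% | 1.08 | 12.8% | 10.9% |
| 95% (equal) | 23.9% | 23.9% | 1.00 | 12.8% | 12.8% |

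For T from 15% to 35% and c from 40% to 80%, the 6-versus-6-month ratio runs from 1.08 to 1.65. A second set of assumptions (T = 10% to 40%, s = 90%, c = 50% to 70%) gives 1.12 to 1.39 for 6 versus 6 months and 1.25 to 1.78 for 3 versus 3 months.

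**Unequal routine capture.** Let pre-switch capture be p instead of c. Take T = 20% (h = 0.2231), s = 90%, c = 50%, so average post-switch capture is (0.9 + 0.5)/2 = 70%.

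- p = 70%: the 6-month ratio is exactly 1.00. Against a 3-month pre-switch incidence of 7.5%, months 0-3 show 9.6% (ratio 1.27) and months 3-6 show 5.4% (ratio 0.72). The pooled window hides both.
- p = 80%: pre = 1 - exp(-0.2231 × 0.8) = 16.3%, post = 1 - exp(-0.2231 × 0.7) = 14.5%, ratio 0.88.

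**Unequal windows.** Setting the 6-month look-back against the 3 card months alone gives ratios of 0.51 to 0.56 when capture is equal (s = c = 90%, T = 10% to 40%), purely from window length. With c = 50% to 70% the ratios are 0.65 to 0.91. Window length therefore has to be fixed together with the split at Month 3.

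**The case against.** The strongest reply is that the mechanism depends on two facts the documents do not give: how the parent studies collected diarrhea, and whether card entries reach the adverse event data. Both gaps are real, and the point is conditional on them. They also show what is missing: whichever way card entries are filed, the SAP does not say whether they count.

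Second, a reader might infer that post-switch incidence must rise and then fall. The documents do not support that. Extension contact is sparse (visits every 6 or 12 months, calls every 3 months, Protocol 6.2), and the contact schedule late in the parent studies is not given. If it was denser, the net ratio can be 1 or lower, as shown above. Nor is there a clean return to routine reporting at Month 3, because the request to contact the doctor is not time-limited. The card itself is an episode log, not a daily diary.

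Third, the comparison is descriptive, with no decision rules (SAP 4.2), and SAP 8.2.2.8 already shows grade over time, so early and later months could be separated. Both statements are correct. No error rate is affected, but the periods are left open and nothing warns the reader that collection changes within them.

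Fourth, if the card raises capture, a finding of no increase would be more reassuring. That holds only if routine capture was similar before and after the switch, and it does not help if an increase is seen.

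Finally, one might rest the formulation conclusion on grade 3 or higher events alone, as less open to prompting. The leaflet's diet and antidiarrheal advice is handed out at the switch and could lower severity, and the EMA question is about incidence. Severe events belong beside all-grade incidence, not in its place.

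**Conclusion.** The point holds in conditional form. Solicited recording by card is confined to the first 3 months on the commercial tablet, no equivalent is described for the parent studies, and the SAP neither separates that period nor says how card-sourced events are handled. If those events enter the adverse event data, the look-back and the parent-versus-extension comparison mix differently ascertained periods and could show an early rise with no true formulation effect.

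The size is not known. A spurious ratio of about 1.1 to 1.6 for 6 versus 6 months follows from assumed capture rates, an assumed constant hazard and equal routine capture on both sides; equal capture throughout gives 1.0, and denser contact in the parent studies could reverse the sign. These figures illustrate what is possible and do not estimate the bias. The consequence is for interpretation of the EMA comparison only.

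**What to change.** In SAP 6.2.7 and 8.2.2.8, for patients who switched from the clinical to the commercial formulation:

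1. Fix the post-switch periods so that months 0-3 (card) are shown separately from months 3-6 and later (no card), each against a pre-switch window of equal length.
2. Where the eCRF identifies card-sourced events, report incidence with and without them as a sensitivity analysis. If it does not identify them, say so. Removing them is not a clean correction, because some would have been reported anyway.
3. Show grade 3 or higher and serious diarrhea for the same windows, alongside all-grade incidence.
4. State the change in collection at the switch and at Month 3 when interpreting the formulation comparison, with a short description of how the parent studies elicited diarrhea.

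The cost is SAP wording and a few more tables, with no new data collection. The shorter windows and the severe-event tables will have few events and wide intervals. The card-source analysis is possible only if the eCRF carries the information.
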